9.2 Secondary Efficacy Variables

The analyses of secondary endpoints will be based on the following

- The mean acute-on-chronic (surge) changes in testosterone and LH levels from just prior to the second injection through 14 days after the second injection of LMIS 25 mg (Days 85-87, week 13; Day 98 [14 days post the second dose], week 14)

An 'acute-on-chronic' change is defined as a >25% increase in testosterone and LH levels compared to the testosterone and LH levels just prior to the second injection. The mean acute-on-chronic (surge) changes in testosterone and LH levels will be analyzed based on subset of subjects have an 'acute-on-chronic' change at Visit 14 (Day 85), Visit 15 (Day 86), Visit 16 (Day 87) and Visit 17 (Day 98). The mean acute-on-chronic (surge) changes in testosterone and LH levels from just prior to the second injection through 14 days after the second injection of LMIS 25 mg (Day 98, week 14) will be summarized descriptively and a paired t-test or Wilcoxon signed-rank test will be used under significance level of 0.05. The summary results will be provided as Table 14.2.4~Table 14.2.5 for ITT population and Table 14.2.16~Table 14.2.17 for PP population.

- Effect of LMIS 25 mg on change of serum prostate-specific antigen (PSA) levels
- Effect of LMIS 25 mg on change of serum LH levels

The serum PSA levels and serum LH levels will be listed by subject in Listing 16.2.6.2 and Listing 16.2.6.3. The change from baseline for serum PSA levels at scheduled visit and serum LH levels at scheduled visit will be summarized descriptively and a paired t-test or Wilcoxon signed-rank test will be used with significance level of 0.05. The summary results will be provided as Table 14.2.6~Table 14.2.7 and Table 14.2.18~Table 14.2.19 for ITT and PP populations. Also, the PSA levels over time will be presented in Figure 14.2.5~Figure 14.2.6 for ITT and PP populations; the LH levels over time will be presented as Figure 14.2.3~Figure 14.2.4 for ITT and PP populations.

Statistical Analysis Plan

- The percentage of subject with PSA relapse defined as after achieving the serum PSA level ≤ 4 ng/mL post LMIS 25 mg injection but with an increase in serum PSA of $>50\%$ PSA nadir by Day 168 (week 24)
- The percentage of subject achieving normal serum PSA level (<4 ng/mL) on Day 168 ± 5 days (week 24)

The subject with PSA relapse is defined as after achieving the serum PSA level ≤ 4 ng/mL post LMIS 25 mg injection but with an increase in serum PSA of $>50\%$ PSA nadir by Day 168 (week 24), i.e. subject achieves the serum PSA level ≤ 4 ng/mL on Day 28 but with an increase in serum PSA of $>50\%$ PSA on Day 84 or Day 168, or subject achieves the serum PSA level ≤ 4 ng/mL on Day 84 but with an increase in serum PSA of $>50\%$ PSA on Day 168.

The incidence of PSA relapse will be presented as subject count, percentage, and exact 95% CI for binomial proportion in [Table 14.2.8](#) and [Table 14.2.20](#) for ITT and PP populations; and the percentage of subject achieves normal serum PSA level will be presented as [Table 14.2.9](#) and [Table 14.2.21](#) for ITT and PP populations. Besides, the additional analyses of PSA levels <4 ng/mL for subjects with elevated PSA at baseline as [Table 14.2.11](#) and [Table 14.2.23](#). It is noted that the normal serum PSA level shall be analyzed as <4 ng/mL rather than <4 ng/dL since it is typo on protocol.

- The percentage of subjects with enhanced serum testosterone concentration suppression to ≤ 20 ng/dL on Day 28 ± 1 day (week 4) and on Day 168 ± 5 days (week 24)

The percentage of subjects with a serum testosterone ≤ 20 ng/dL on Day 28 ± 1 day (week 4) and on Day 168 ± 5 days (week 24) will be analyzed using a standard large sample normal approximation to a Binomial distribution. The summary results included subject count, percentage and exact 95% CI for binomial proportion will be presented as [Table 14.2.10](#) and [Table 14.2.22](#) for ITT and PP populations.

Based on protocol, the testosterone level is assessed at Week 26 for the first enrolled 30 subjects. The additional analysis of subjects with a serum testosterone concentration suppressed to castrate levels (≤ 50 ng/dL) at Week 26 will be presented as [Table 14.2.12](#) and [Table 14.2.24](#) for ITT and PP populations.

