7.2. Efficacy Assessment

Efficacy assessments will be performed based on the study schedule (Table 1a and 1b). The primary endpoint of efficacy is to determine the percentage of subjects with a serum testosterone concentration suppressed to castrate levels (≤ 50 ng/dL) on Day 28 ± 1 day (week 4) following the first injection of LMIS 25 mg, and the proportion of subjects with serum testosterone suppression (≤ 50 ng/dL) from Day 28 ± 1 day (week 4) through Day 168 ± 5 days (week 24) until the end of the study.

The proportion of subjects exhibiting post-suppression breakthrough of serum testosterone to > 50 ng/dL from Day 28 ± 1 day (week 4) through Day 168 ± 5 days (week 24) until the end of the study will also be determined.

The secondary endpoints will determine the mean acute-on-chronic changes in serum testosterone level before injection of the second dose LMIS 25 mg on Day 84 (week 12) and on Days 85, 86, 87 (week 13), and 98 (2 weeks post the second injection). The percentage of subjects observed with acute-on-chronic (surge) effect on serum testosterone and LH levels just before the second dose administration and on Day 1 to Day 3 (Days 85, 86, 87) and 14 days (Day 98) post the second injection of LMIS 25 mg will be analyzed.

The effect of LMIS 25 mg on serum LH levels and the percentage of subjects with enhanced serum testosterone concentration suppression to ≤ 20 ng/dL on Day 28 ± 1 day (week 4) and on Day 168 ± 5 days (week 24) by LMIS 25 mg administration will also be determined. In addition, the effects of LMIS 25 mg on the percentage of subject with PSA relapse and the percentage of subjects that achieves normal serum PSA level will be determined at the end of study.

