10.4.2. Analysis of secondary endpoints

The analyses of secondary endpoints will be based on the following:

- The mean acute-on-chronic (surge) changes in testosterone and LH levels from just prior to the second injection through 14 days after the second injection of LMIS 25 mg (Day 98, week 14)

The mean acute-on-chronic changes in serum testosterone concentration will be summarized by descriptive statistics. The change from baseline will be summarized descriptively and a paired t-test or Wilcoxon signed-rank test will be used, data significance level of 0.05.

- Effect of LMIS 25 mg on change of serum prostate-specific antigen (PSA) levels
- Effect of LMIS 25 mg on change of serum LH levels

The serum PSA levels and serum LH levels during the study will be summarized as descriptive statistics. The mean acute-on-chronic changes in LH level from after the 2nd injection of LMIS 25 mg will be summarized descriptively. The change from baseline will be summarized descriptively and a paired t-test or Wilcoxon signed-rank test will be used, data significance level of 0.05.

- The percentage of subject with PSA relapse defined as after achieving the serum PSA level ≤ 4 ng/mL post LMIS 25 mg injection but with an increase in serum PSA of $>50\%$ PSA nadir by Day 168 (week 24). A post hoc analysis will be performed to determine the incidence of PSA recurrence.

The incidence of PSA relapse is defined as after achieving serum PSA level ≤ 4 ng/mL post LMIS 25 mg injection but with an increase in serum PSA $> 50\%$ compared with nadir will be presented as a count, percentage, and 95% CI.

- The percentage of subject achieving normal serum PSA level (<4 ng/dL) on Day 168 ± 5 days (week 24)

The number of subjects achieving normal serum PSA level (<4 ng/dL) on Day 168 ± 5 days (week 24) will be presented as a count, percentage, and 95% CI.

Version: 1.1

Date: 24-Nov-2017

Protocol No.: FP01C-17-001

- The percentage of subjects achieving enhanced serum testosterone concentration suppression to ≤ 20 ng/dL on Day 28 ± 1 day (week 4) and on Day 168 ± 5 days (week 24).

The percentage of subjects with an enhanced serum testosterone suppression to ≤ 20 ng/dL by Day 28 ± 1 day (week 4) and Day 168 ± 5 days (week 24) will be analyzed using a standard large sample normal approximation to a Binomial distribution.

Table 5 Data Censoring Rules

Subject Discontinued	Day 28- 168 or Day of Discontinuation		To Be Handled As
	More Than 1 Missing Testosterone Value	Any Escape	

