1. INTRODUCTION

This is a multi-national, multi-center, open-label, single-arm and phase III study to determine the efficacy, safety, and pharmacokinetic profile of LMIS 25 mg in patients with prostate cancer. Approximately 133 subjects will be enrolled in this study.

This statistical analysis plan (SAP) is based on protocol version 1.1, dated 20-Nov-2017. The SAP provides details of data handling procedures and statistical analysis methods for efficacy and safety evaluations. It also outlines statistical programming specifications for tables, listings and figures, and other details on the analyses not provided in the study protocol. It is noted that in case there is discrepancy between the SAP and the protocol then the SAP will supersede the protocol.

This SAP will include efficacy and safety analysis only. The pharmacokinetic (PK) analysis plan is not part of this SAP.

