4. GENERAL STATISTICAL ISSUES

For data listings, all raw data will be displayed exactly as provided. Partial date(s) will be listed as provided in the listings. The partial date(s) will be imputed when using for calculation. For the start date, a missing month is supplied a default value of January and a missing day is supplied a default value of 1. For the stop date, a missing month is supplied a default value of December and a missing day is supplied a default value of the last day of the month. The Baseline is defined as the last observation prior to first dose unless otherwise specified.

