4.1 Continuous endpoints

Continuous variables will be summarized and presented as number of observations, mean, standard deviation (SD), median, range, Hodges-Lehmann estimator, and 95% CI. Changes from baseline

will be tested by paired t-test or Wilcoxon signed-rank (if data violated the normal assumption, i.e. the p-value of test of normality is <0.05) test for continuous variables using a significance level of 0.05. For summaries of quantitative data, the median, minimum and maximum value will be reported exactly as the raw data are reported; measures of central tendency (means will be reported as one decimal more than the raw data and measure of variance (SD) will be reported as the two decimals more than the raw data.

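### SAP 9.2 tests the mean change after the second injection only in subjects picked for a rise of more than 25%, so the estimate and p-value do not address whether levels rise on average

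*SAP*

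**What the plan says.** SAP 3.3 and protocol 2.2.2.1 define the endpoint as the mean change in testosterone and LH from just before the second injection through 14 days after it (Days 85, 86, 87 and 98). Neither restricts it to particular subjects.

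For the analysis, protocol 10.4.2 says "The mean acute-on-chronic changes in serum testosterone concentration will be summarized by descriptive statistics" and adds a paired test of change from baseline, again with no threshold and no subset. Protocol 7.2 separately plans to analyse "The percentage of subjects observed with acute-on-chronic (surge) effect on serum testosterone and LH levels".

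SAP 9.2 differs. An acute-on-chronic change "is defined as a >25% increase in testosterone and LH levels compared to" the levels just before the second injection. Then: "The mean acute-on-chronic (surge) changes in testosterone and LH levels will be analyzed based on subset of subjects have an" acute-on-chronic change at Visits 14 to 17. The next sentence says that the mean changes "will be summarized descriptively and a paired t-test or Wilcoxon signed-rank test will be used under significance level of 0.05". One pair of tables is named per population: 14.2.4 and 14.2.5 for ITT, 14.2.16 and 14.2.17 for PP. No other analysis set is named.

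SAP 1 settles which text governs: "in case there is discrepancy between the SAP and the protocol then the SAP will supersede the protocol".

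**The concern.** The 25% rise that admits a subject to the analysis is a rise in the same variable whose mean change is then estimated and tested. Ordinary within-subject and assay variation will put some subjects above the threshold, and averaging only those subjects gives a rise whether or not levels move on average.

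The SAP also leaves open how the subset is formed: separately at each visit, on a rise at any of the four visits, or on a rise at all four; and for each hormone separately or for both together. Every reading conditions on a rise.

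The rest of the SAP does not fill the gap:

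- **LH.** SAP 9.2 summarises change from baseline at scheduled visits, but SAP 4 says "The Baseline is defined as the last observation prior to first dose unless otherwise specified". Those tables compare with the value before the first injection, not the second.
- **Testosterone.** There are by-subject listings and counts against thresholds, but no summary of mean change.
- **Percentage with a surge.** The SAP specifies no table for the proportion planned in protocol 7.2.

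At stake is a valid estimate of the mean change around the second dose, chiefly for testosterone. As planned, the report would show a mean surge and a small p-value that noise alone can produce.

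**Working it through.** The documents give no power or expected size for this analysis, so there is no figure of the plan's to reproduce.

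**Step 1: what follows without any assumed variability.** If subjects are selected by the rise at the visit tested, or at all four visits, every analysed change is positive. The exact two-sided Wilcoxon signed-rank p-value with n positive changes is 2 × 0.5^n:

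- n = 5: 2 × 0.03125 = 0.0625
- n = 6: 2 × 0.015625 = 0.031

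Six or more selected subjects therefore give p<0.05 whatever the data in everyone else show. Under any-visit selection the change at a given visit can be negative, so the sign is not forced, but the mean is biased upward.

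**Step 2: how many subjects noise alone selects.** Inputs: N = 120 (SAP 4.4, the evaluable sample size); threshold 1.25 (SAP 9.2); within-subject CV assumed, 5% to 30%. With log-normal values and no true change, the share rising more than 25% at one visit is 1 − Φ(ln 1.25 / (s√2)), where s² = ln(1 + CV²). At CV 20%, s = 0.198 and ln 1.25 = 0.223, so 0.223 / 0.280 = 0.797. The share is 21.3%, or 25.5 of 120. At CV 10% it is 5.7%, or 6.8 of 120.

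**Step 3: how often the planned test is significant.** 2,000 simulated trials per CV, N = 120, one value before and four values after the second dose, same true mean throughout. Assumed level 10 ng/dL and between-subject log-SD 0.4. The test is of the change at the first visit after the second dose. SAP 4.1 selects Wilcoxon "if data violated the normal assumption, i.e. the p-value of test of normality is <0.05" and otherwise the t-test; Shapiro-Wilk is assumed because the SAP names no normality test. Subsets of fewer than 3 count as not significant. Each cell shows the mean number selected and the percentage of trials with p<0.05.

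| CV | Rise at that visit | Rise at any visit | Rise at all four |
|---|---|---|---|
| 5% | 0.1; 0% | 0.4; 0% | 0; 0% |
| 8% | 2.9; 42% | 9; 86% | 0.1; 0% |
| 10% | 6.7; 92% | 19; 99% | 0.4; 1% |
| 15% | 17; 100% | 42; 100% | 2; 24% |
| 20% | 26; 100% | 56; 100% | 4.5; 65% |
| 30% | 35; 100% | 70; 100% | 8; 94% |

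With all 120 subjects and the same rule, p<0.05 occurs in 4% to 7% of trials at every CV. Repeat runs agree with the table to within 3 percentage points.

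The mean of the individual percentage changes in the same-visit subset is +40% at CV 15%, +48% at 20% and +66% at 30%. In the any-visit subset it is +17% to +30% for CV 10% to 30%. The true change is zero in each case.

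**Step 4: a true fall.** Multiply the post-dose mean by 0.90. The same-visit subset shows:

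- CV 15%: 7 selected, mean +37%, p<0.05 in 93% of trials
- CV 20%: 14 selected, mean +45%, 100%
- CV 30%: 26 selected, mean +62%, 100%

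At CV 20% the all-subject test correctly shows a significant fall in 97% of trials.

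**The case against.** **The SAP may only mean to describe surge size among subjects who had one.** That is a coherent description. It does not justify a p-value against zero change, and it leaves the endpoint in SAP 3.3 without an analysis.

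**A single uncontrolled arm cannot show that the second dose causes a change.** This is right, and it applies to the all-subject test too. The point is confined to estimating the mean change after the second dose.

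**Other output covers the ground.** In part. LH means before and after the second dose can be read side by side from the scheduled-visit tables, though no paired comparison spans the injection. Testosterone excursions above 50 ng/dL are tabulated by visit in Tables 14.2.3 and 14.2.15, so no further analysis of that kind is needed. Neither gives a mean testosterone change. The separate PK plan is not available, and protocol 10.6 describes PK/PD follow-up in the first 30 subjects; the supportable statement is that this SAP specifies no all-subject analysis of the change.

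**SAP silence does not cancel the surge percentage in protocol 7.2, and the number selected will appear as the count of observations.** True, but the percentage, its interval and the rule for counting a subject remain undefined.

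**The size depends on assumed CVs and on the reading.** This stands. At CV 5%, or with all four visits required at CV 10%, few subjects are selected and the test rarely rejects. The percentages carry over to LH only where the log-normal model holds; values near a quantitation limit could behave differently. N = 120 is the planning figure, whereas SAP 4.4 also reports 144 enrolled; at a given CV the number selected would scale by up to 144/120 = 1.2.

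**The stakes are low.** Agreed in direction: the bias overstates an unwanted effect, and study success rests only on the Day 168 lower confidence bound in SAP 9.1.

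**Conclusion.** The concern holds. SAP 9.2 conditions the estimate and test on the outcome, departs from the endpoint definition and from protocol 10.4.2, and prevails over the protocol. Under same-visit selection, or selection at all four visits, six selected subjects force an exact Wilcoxon p of 0.031 with no assumption about variability. For CVs of 10% and above, same-visit or any-visit selection turns null data into a significant surge in 92% to 100% of simulated trials, against about 5% when all subjects are tested; requiring all four visits gives 1% to 94% over the same CVs. These rates rest on the assumed CV range, the log-normal model and N = 120. The defect affects one secondary endpoint, cannot produce a false efficacy claim and leaves the primary criterion alone. It should be fixed because, without the change, the SAP provides no valid estimate of the mean change around the second dose, chiefly for testosterone.

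**What to change.** In SAP 9.2:

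1. Summarise and test the change from the pre-second-injection value at Days 85, 86, 87 and 98, separately for testosterone and LH, in all ITT and PP subjects who received the second dose and have paired values. Name the pre-second-injection value as the baseline for this analysis.
2. Report the number and percentage with a rise of more than 25%, with exact 95% CI, as the analysis that protocol 7.2 calls for. State whether a subject counts per visit or on any visit, and that each hormone is classified separately.
3. Keep the mean change among those subjects, if wanted, as description without a p-value.

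The cost is SAP wording and a changed analysis set for Tables 14.2.4, 14.2.5, 14.2.16 and 14.2.17. No new data are needed.

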In the Phase III study (study number FP01C-13-001), a total of 137 subjects were enrolled and received at least one dose of the study drug (ITT population), and 124 subjects completed the study without major protocol violations that would affect the primary efficacy endpoint (per-protocol population (PP)). The primary efficacy endpoint was achieved in 97.0% of subjects in both ITT and PP populations. The 95% confidence interval from Kaplan-Meier estimates was (92.2%, 98.9%), and the 95% Repeated-Confidence Interval (RCI) was (92.5%, 99.4%). By Day 28, mean testosterone concentration was suppressed below the castrate level to 17.6 ng/dL, and the

Version: 1.1

Date: 24-Nov-2017

Protocol No.: FP01C-17-001

suppression rate was 98.5% (135 out of 137 subjects achieved medical castration). No mean increase in testosterone was observed after the second injection. Four subjects did not have successful suppression of testosterone by the primary efficacy endpoint analysis, two of whom failed to achieve castration level on Day 28 and the other two had transient testosterone escapes.

The secondary endpoints of this study were to determine the effect of LMIS 50 mg on (1) the proportion of subjects exhibiting post-suppression excursions of serum testosterone to > 50 ng/dL, either through “breakthrough” (i.e., episodes unrelated to LMIS 50 mg dosing), or through the “acute-on-chronic” surge (i.e., related to the second dose of LMIS 50 mg), (2) the effect of LMIS 50 mg on serum PSA levels, (3) the effect of LMIS 50 mg on serum LH levels.

In the FP01C-13-001 study, only two subjects exhibited post-suppression excursions. These post-suppression excursions occurred after the second dose of LMIS 50 mg injection on Day 168 to Day 171. These effects were attributed to mild, transient acute-on-chronic surge. Serum testosterone levels in all the above subjects returned to below the castrate level shortly thereafter. No other breakthrough of serum testosterone to > 50 ng/dL was observed in this study.

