Additional safety assessments include vital signs, physical examinations, local injection site reaction, assessments of bone pain, urinary signs, and symptoms, and laboratory assessments.

All concomitant medication used during the study period will be recorded in the CRF until the end of the study.

Pharmacokinetic assessments of serum leuprolide levels will be performed using a validated liquid chromatography-tandem mass spectrometry (LC/MS/MS) method. To evaluate the sustained castration testosterone level after two doses of LMIS 25 mg injections, the first 30 subjects will have extended sampling time points to establish the full PK/PD profile of serum leuprolide by collecting blood samples on Day 0 (prior to the first dose of LMIS 25 mg, and at 2, 4, and 8 hours post-dose), Days 1, 2, 3, 7, 14, 21, 28, 42, 56, 77, 84 (week12: prior to the second dose and at 2, 4,

Protocol No.: FP01C-17-001

and 8 hours post the second dose), Days 85, 86, 87, 98, 112, 126, 140, 161, 168 (week 24) and 182 (week 26, end of study (EOS)).

The remaining approximately 103 subjects will have blood samples collected for determining the serum leuprolide on Day 0 (prior to the first dose of LMIS 25 mg, and 4 hours post the first dose), Days 1, 3, 14, 21, 28, 56, 77, 84 (week 12: prior to the second dose and 4 hours post dose), 85, 86, 87, 98, 112, 140, 161, and 168 (week 24/end of study (EOS)).

The pharmacokinetic parameters of leuprolide will be determined during the study period using non-compartmental approaches with Phoenix WinNonlin[®], including C_{max} , T_{max} , C_{week4} , C_{week12} , $AUC_{0-week4}$, $AUC_{0-week12}$, $C_{avg(0-12week)}$ after each dose. The Day 182 (week 26) leuprolide serum concentration data from the first 30 subjects will also be determined.

Serum testosterone and LH levels will be determined in all subjects using blood samples collected at the specified time points along with serum leuprolide analysis.

Blood samples for determining the extended PK/PD profile of serum testosterone concentrations will be collected in the first enrolled 30 subjects on Day 0 (prior to the first dose of LMIS 25 mg and 2 h, 4 h, and 8 h post dose), Days 1, 2, 3, 7, 14, 21, 28, 42, 56, 77, 84 (week 12: prior to the second dose and 2 h, 4 h, and 8 h post dose), Days 85, 86, 87, 98, 112, 126, 140, 161, 168 (week 24) and Day 182 (week 26).

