For determining the serum testosterone concentration in the remaining 103 subjects, blood samples will be collected on Day 0 (prior to the first dose of LMIS 25 mg and 4 hours post dose), Days 1, 3, 14, 21, 28, 56, 77, 84 (week 12: prior to the second dose of LMIS 25 mg and 4 hours post dose), 85, 86, 87, 98, 112, 140, 161, and 168 (week 24/end of study (EOS)).

Blood samples for determining the serum LH concentrations will be collected on Day 0 (prior to the first dose of LMIS 25 mg), Days 1, 2, 3, 7, 14, 21, 28, 42, 56, 77, 84 (week 12, prior to the second dose of LMIS 25 mg), 85, 86, 87, 98, 112, 126, 140, 161, 168 (week 24; end of study) in the first enrolled 30 subjects.

For determining the serum LH concentration in the remaining 103 subjects, blood samples will be collected on Day 0 (prior to the first dose of LMIS 25 mg), Days 1, 3, 14, 21, 28, 56, 77, 84 (week 12: prior to the second dose of LMIS 25 mg), 85, 86, 87, 98, 112, 140, 161, and 168 (week 24/end of study (EOS)).

Serum testosterone concentrations will be measured using a validated LC/MS/MS method. The method validation follows the European Medicines Agency (EMA) Guideline on Bioanalytical Method Validation (EMA/CHMP/EWP/192217/2009) and the FDA Guidance for Industry: Bioanalytical Method Validation, May 2001.

The measurement of serum LH concentrations will be performed using validated, commercial assay kits at the BA lab.

For subjects who terminate early or withdraw, phone contacts will be performed at 12 weeks after the last injection of the investigational product (IP) to collect information concerning drug-related AEs, concomitant medication, non-drug therapy received for AE treatment, disease progression status, and subject survival status.

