- ⁶ Testosterone samples will be collected in the morning at specified time points as shown in the above schedule. On dosing days (Day 0 and Day 84), blood samples for testosterone analysis will be collected before LMIS 25 mg administration. Serum testosterone levels will be analyzed at the QPS Bioanalytical Lab. For fast turn-around of assay results, a sample for the screening testosterone will also be sent to the Central Lab. After that, additional samples for testosterone may be ordered by the investigator at their discretion and analyzed at the Central Lab using commercial diagnostic assays for fast turn-around of results.
- ⁷ LH samples will be collected in the morning at specified time points as shown in the above schedule. On dosing days (Day 0 and Day 84), blood samples for LH analysis will be collected before LMIS 25 mg administration. Serum samples for LH concentrations will be analyzed at the BA lab using a validated ELISA method. More frequent tests of LH may be ordered by the investigators at their discretion, and these samples can be analyzed at the Central Lab for a faster data turn-around. Serum samples to the BA Lab will be batched and shipped periodically.
- ⁸ Hematology tests include CBC, Hb, Hct, RBC count, WBC count with differential and platelet count.
- ⁹ Biochemistry tests include ALT, AST, ALP, total bilirubin, BUN, Serum Cr, electrolytes (K, Na, Mg, Ca and P), blood glucose, and lipid profile (LDL, HDL, triglycerides)
- ¹⁰ Urinalysis tests include pH, specific gravity, leukocyte, erythrocyte, urine glucose, nitrate, and protein.

Note: Regarding the time window for blood sample collection, at 2, 4, 8 hours post LMIS 25 mg administration on Day 0 (Visit 1) and Day 84 (Visit 13), a 15-minute time window is allowed; at Visits 6 to 9 (Day 7 to Day 28), a \pm 1-day window is allowed. At Visits 10 and 12 (Day 42 to Day 77), a \pm 3-day window is allowed. At Visits 13 to 16 (Day 84, for the second dose injection, week 12, to Day 87), only \pm 1-day window is allowed. At Visits 17 to 21 (Day 98 to Day 161), a \pm 3-day window is allowed. At Visits 22 (Day 168), a \pm 5-day window is allowed. At Visit 23 (Day 182), a \pm 3-day window is allowed.

Protocol No.: FP01C-17-001

Table 1b Study Schedule Visits 14-EOS

	Follow Up								EOS/ET ⁺	PK-extended Follow up
Visit	14	15	16	17	18	19	20	21	22	23#
Week	13	13	13	14	16	18	20	23	24	26
Day	85*	86*	87*	98*	112*	126#	140	161	168	182#
Concomitant treatments ²	X	X	X	X	X	X#	X	X	X	X#

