6.13. Visit 13 (Day 84 ± 1 day; 2nd Dose Administration; week 12)

The following procedures and sample collection should be performed at this visit:

1. Conduct physical examination and record vital signs (including body weight) prior to dosing.
2. Perform ECG prior to dosing and at 4-hour post-dosing.
3. Collect blood sample prior to dosing for analysis of:

Protocol No.: FP01C-17-001

- Hematology: CBC, including Hb, Hct, RBC count, WBC count, WBC differential and platelet count
 - Biochemistry: ALT, AST, ALP, total bilirubin, BUN, Serum Cr, electrolytes (K, Na, Mg, Ca, and P), blood glucose, lipid profile (LDL, HDL, triglycerides)
 - PSA level
 - Collect urine sample prior to dosing for urinalysis: pH, specific gravity, leukocyte, erythrocyte, protein, urine glucose, and nitrate.
4. Collect serum samples for pharmacokinetic analysis of leuprolide mesylate and testosterone prior to dosing and at 2, 4, and 8 hours post-dosing in the first enrolled 30 subjects. Collect serum samples prior to dosing and at 4 hours post-dosing in the remaining 103 subjects for pharmacokinetic analysis of leuprolide mesylate and testosterone.
 5. Collect serum samples for LH prior to dosing.
 6. Assess bone pain prior to dosing.
 7. Assess urinary signs and symptoms prior to dosing.
 8. Record concomitant medication(s) prior to dosing and post dosing.
 9. Record AE(s) prior to dosing and post dosing.
 10. Administer LMIS 25 mg (second administration).
 11. Investigator to assess local injection site reaction post dosing.

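### The second-injection surge analysis starts at Day 85, so a testosterone rise of more than 25% seen only in the Day 84 post-dose samples does not appear as a surge

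*SAP*

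**What the plan says.** **Window.** SAP 9.2 (Secondary Efficacy Variables) sets the surge endpoint as the change in testosterone and LH "from just prior to the second injection through 14 days after the second injection of LMIS 25 mg".

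**Threshold.** "An 'acute-on-chronic' change is defined as a >25% increase in testosterone and LH levels" over the value just before the second injection.

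**Time points.** The mean change is taken in the subset of subjects with such a "change at Visit 14 (Day 85), Visit 15 (Day 86), Visit 16 (Day 87) and Visit 17 (Day 98"). No Day 84 post-dose time is named. Protocol 2.2.2.1 and 7.2 name the same days. The protocol synopsis and 10.4.2 give only Day 98, as the end of the window.

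**Sampling.** For the first 30 subjects, Protocol 3.1 schedules testosterone on Day "84 (week 12: prior to the second dose and 2 h, 4 h, and 8 h post dose"). For the remaining 103 it schedules Day "84 (week 12: prior to the second dose of LMIS 25 mg and 4 hours post dose"). Protocol 6.13 repeats this at Visit 13: "Collect serum samples prior to dosing and at 4 hours post-dosing in the remaining 103 subjects for pharmacokinetic analysis of leuprolide mesylate and testosterone". SAP 3.1 carries the same schedule. LH on Day 84 is drawn before dosing only.

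**Footnote 6** of the visit schedule (Protocol Table 1a, repeated in SAP Table 3.1-1) reads differently: "On dosing days (Day 0 and Day 84), blood samples for testosterone analysis will be collected before LMIS 25 mg administration".

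**Background.** Protocol 1.3 reports two subjects with excursions above 50 ng/dL in the 50 mg study: "These post-suppression excursions occurred after the second dose of LMIS 50 mg injection on Day 168 to Day 171". It attributes them to a mild, transient acute-on-chronic surge.

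**The concern.** The stated window opens before the injection, yet the first analysed value comes a day later. Visit 14 is Day 85 ± 1 day, so it can fall up to two days after a Day 84 injection (86 − 84 = 2).

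Because subjects enter the analysis through the >25% rule at the named visits, the loss is complete for some of them. A man whose testosterone rises by more than 25% at 4 h and is back by Day 85 is neither counted as having a surge nor included in the mean change. The surge tables would then understate how often the second injection provokes a rise, although the samples that could show it are already scheduled.

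**Working it through.** The plan attaches no figure to this endpoint. Its one computed design figure, 85% power with 120 subjects (Protocol 10.1, SAP 4.4), concerns the primary endpoint. By exact binomial, the smallest rejection count at one-sided 0.025 against 0.90 is 115 of 120, with actual level 0.0160 and power 0.847 at 0.97. That reproduces, and nothing below changes it.

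**1. Scheduled testosterone samples after the second injection, through Day 98** (Protocol 3.1 and 6.13, SAP 3.1)

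- Remaining 103 subjects: 4 h, Days 85, 86, 87, 98 = 5 per subject
- First 30 subjects: 2 h, 4 h, 8 h, Days 85, 86, 87, 98 = 7 per subject
- Named in SAP 9.2: Days 85, 86, 87, 98 = 4 per subject

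The surge analysis leaves out 1 of 5 per subject in the 103 and 3 of 7 in the first 30.

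**2. Totals with 133 subjects**

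- Scheduled: 103 × 5 + 30 × 7 = 515 + 210 = 725
- Named: 133 × 4 = 532
- Left out: 103 × 1 + 30 × 3 = 193, and 193 / 725 = 26.6%

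**3. Totals with the 144 enrolled** (SAP 4.4; assumes 114 + 30)

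- Scheduled: 114 × 5 + 30 × 7 = 570 + 210 = 780
- Left out: 114 × 1 + 30 × 3 = 204, and 204 / 780 = 26.2%

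These are counts by schedule, with every subject receiving the second dose and attending.

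**4. Does the >50 ng/dL rule cover the same ground?** SAP 9.1 counts any testosterone above 50 ng/dL between Days 28 and 168 as an escape, so a Day 84 post-dose value above 50 is an event. The surge threshold is far lower. As an illustration only, take the 50 mg study's Day 28 mean of 17.6 ng/dL (Protocol 1.3) as the pre-injection level:

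- A 25% rise: 17.6 × 1.25 = 22.0 ng/dL
- Rise needed to reach 50: 50 / 17.6 = 2.84 times

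A dosing-day rise between these two levels meets the surge definition, is not an escape, and appears in neither analysis.

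**5. Timing in the 50 mg study.** Doses were 6 months apart (Protocol 1.3). If its second dose fell on Day 168, then Days 168 to 171 correspond to Days 84 to 87 here. Three of those four days (85, 86, 87) are analysed. The text does not say on which day either excursion began or ended.

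**The case against.** The strongest reply is that the SAP follows the protocol. Protocol 2.2.2.1 and 7.2 list Days 85 to 87 and Day 98, so the SAP did not drop time points that the protocol had assigned to this endpoint. That stands, and it is why the named-day summary should remain the prespecified analysis. It does not close the gap between those days and the window that both documents state.

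There are also sound reasons for the chosen days. The schedule asks for morning samples, and a 4 h or 8 h draw may fall later in the day than its pre-dose reference. The endpoint covers testosterone and LH together, and LH has no Day 84 post-dose sample. Both points argue for separate labelling rather than for omission.

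Several stronger readings are tempting, and the documents do not support them:

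- **The 50 mg study shows that the surge occurs within hours.** It does not. Its excursions are consistent with an early surge, but Day 168 as the dosing day is inferred. Nothing says that either excursion fell on that day or had resolved by the next.
- **The samples are discarded.** They are not. Testosterone is listed by subject and visit (Listing 16.2.6.1), and SAP 11.5 relates time-matched testosterone to the ECG, which is recorded at 4 h on dosing days.
- **The surge tables and the Kaplan-Meier analysis contradict each other.** They use different definitions (>25% against >50 ng/dL) and may legitimately differ.
- **Footnote 6 would lead sites to skip the draws.** This is speculation. Protocol 6.13 and the schedule columns state the draws explicitly, and the SAP reports 144 subjects already enrolled.
- **LH should be assayed on the 4 h serum.** The documents give no basis for assuming that usable serum remains.

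**Conclusion.** The gap is real and modest. For testosterone, the surge analysis omits the dosing-day part of the window it defines: one scheduled sample in every subject and three in each of the first 30, about 26% to 27% of scheduled post-injection samples through Day 98. What can be missed is a rise above 25% seen only on Day 84. How many subjects would show one cannot be estimated from the documents. The primary endpoint, success rule, sample size and power are untouched, because a value above 50 ng/dL is still an escape whenever on Day 84 it was drawn. This is a cheap improvement to a secondary description. It is not an error in the main analysis, and the SAP does not depart from the protocol's named days. The counts assume full attendance and, for 144 subjects, a 114 + 30 split.

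**What to change.** **Surge tables.** For testosterone only, add Day 84 4 h (all subjects) and Day 84 2 h and 8 h (first 30) as separately labelled time points in the ITT tables (within 14.2.4 and 14.2.5) and the PP tables (within 14.2.16 and 14.2.17). Use the pre-dose Day 84 value as reference. At each time, give the number with a value, the number and percentage with a rise above 25%, and the mean change. Keep the Day 85, 86, 87 and 98 summary unchanged as the prespecified analysis.

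**Table note.** State that these draws may be later in the day than the morning reference, that no matching LH value exists, and that the 2 h and 8 h rows cover the first 30 subjects only.

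**Footnote 6.** As a wording correction in both documents, reconcile it with the 2, 4 and 8 h testosterone columns, for example by saying that the reference sample is pre-dose and the marked post-dose samples follow.

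**Cost.** Up to three extra rows per testosterone table, one note and one footnote, from results the study already schedules. No new sample or assay is needed. The small price is that the added rows are harder to interpret than the morning visits, which the note addresses.
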